6.2 DATA MANAGEMENT SYSTEM

Data management will be conducted in compliance with TASC SOPs on Data Management, including TASC SOP33 Data Management to GCP standards and TASC SOP53 Data Management Systems in Clinical Research.

The data management system (DMS) will be Excel. The data will be used to calculate the treatment rate and cure rate for the time period and the rate of new infection. The core data will then be destroyed. The anonymized dataset may be shared with colleagues in other UK Universities. The database is managed in line with all applicable principles of medical confidentiality and UK law on data protection, namely, the Data Protection Act 1998, which brought UK law into line with the EU Data Protection Directive. The Data Controller will be the University of Dundee and the Data Custodian will be the CI.

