3 STUDY OBJECTIVES & OUTCOMES

Table 1: Primary Objectives and Outcome Measures

Primary Objective:	Outcome Measure:	Timepoint of outcome measured
To demonstrate treatment as prevention reduces HCV.	HCV testing in NHS Tayside	Annually

Table 2: Secondary Objectives and Outcome Measures

Secondary Objective:	Outcome Measure:	Timepoint of outcome measured
To develop the analytic framework that can be used to assess the impact of treatment as prevention, incorporating evidence from multiple sources and taking into account uncertainty and bias	Numbers of patients engaged in treatment and SVR ₁₂ during the treatment phase	Years 1-3
To develop dynamic cost-effectiveness models of HCV treatment among PWID	Costs of treatment pathways and infection rates	Year 5
Re-infection with HCV following treatment	Annual routine offer of HCV testing	Following treatment and subsequently annually for each PWID

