6 DATA COLLECTION & MANAGEMENT

6.1 DATA COLLECTION

Details of all patients who are undergoing or have completed HCV treatment in Tayside are entered into a clinical database as per standard care by specialist HCV nurses and this practice will continue as we intensify treatment rates through our clinical trials and NHS treatment pathways. Data in this database will form the source for treatment initiation and outcomes. Twice a year the number of patients treated and cured since last data extraction will be extracted with no patient identifiable information but with data on viral genotype, stage of liver disease, pathway of treatment delivery and current drug use status.

Data on infection rates from routine HCV testing within NHS Tayside is also collected in the virology service in Tayside for government reporting. On a six monthly basis we will extract data on known HCV negative patients who have been retested in that time period. The data extraction will consist of the date when they were last known to be negative, the date of re-test and the result of the test. No patient identifiable data will be used.

Population level data will be collected 6 monthly around the anniversary of the study commencement or to coincide with the NESI data collection cycles.

The source data will be accessed by the clinical care team and clinical data which is not patient identifiable entered into the study data management system which will be built within Excel and held on a University server that is GCP compliant; regularly backed-up, has access controls and updates to operating system and security software. Caldicott approvals will be obtained as required.

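### The half-yearly cure rate in section 6.2 has no stated denominator and no treatment date behind it, so it can show a false trend while treatment numbers are changing

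*Combined protocol and SAP*

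**What the plan says.** Treatment data (section 6.1): "Twice a year the number of patients treated and cured since last data extraction will be extracted with no patient identifiable information". The accompanying fields are "viral genotype, stage of liver disease, pathway of treatment delivery and current drug use status". No date of start, completion or SVR12 is listed. The same paragraph says of data entry that "this practice will continue as we intensify treatment rates", so treatment numbers are expected to change.

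Re-test data (section 6.1): for known negatives who are retested, the extract does carry dates, namely "the date when they were last known to be negative, the date of re-test and the result of the test".

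Use of the data (section 6.2): "The data will be used to calculate the treatment rate and cure rate for the time period and the rate of new infection". No denominator is given for the cure rate, here or in section 7.2. The next sentence is "The core data will then be destroyed", followed by "The anonymized dataset may be shared with colleagues in other UK Universities". The protocol defines neither the core data nor the contents of the anonymised dataset.

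Outcome (section 3, Table 2): "Numbers of patients engaged in treatment and SVR" at 12 weeks, measured in Years 1-3. The abbreviations list places SVR12 at least 12 weeks after the end of treatment.

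**The concern.** A cure cannot be recorded until the course has finished and at least 12 more weeks have passed. With a 26-week window, many of the cures counted in one extract belong to patients who started, or even completed, in the previous one. Dividing the window's cures by the window's treated patients therefore mixes two groups. The error cancels when numbers are steady, but the plan is to intensify treatment, and Table 2 looks at SVR12 in Years 1-3. A period cure rate could then look poor during expansion and recover, or even exceed 100%, as numbers fall, with no change in how well treatment works. Without a treatment date in the extract, an analyst could not correct this from the study file.

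The destruction sentence raises a second, smaller question. Section 7.2 rests the primary outcome on a final evidence synthesis, and section 8.2 sends Tayside incidence to a multi-region comparison. Both may need infections and time at risk placed in the right calendar period, and section 6.2 does not say whether what is needed for that is kept.

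**Working it through.** The plan states no figure on this point, so there is none to reproduce. The check asks what a same-window ratio would show.

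**Inputs**
- Window: 26 weeks (section 6.1, twice a year).
- End of treatment to SVR12: at least 12 weeks (abbreviations list); 12 is used.
- True cure proportion p = 0.90 (section 1 gives over 90% with adequate compliance).
- Course length: not given; assumed 8 or 12 weeks.
- Growth factor g in patients treated from one half-year to the next: not given; assumed 0.8 to 1.5.

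**Formula.** Let N(k) patients be treated in window k, spread evenly, with N(k) = g × N(k-1). Let L be the lag in weeks from the event that defines treated to SVR12, and s = L/26. Cures recorded in window k are p × [(1 - s) × N(k) + s × N(k-1)]. Dividing by N(k):

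Apparent cure rate = p × [(1 - s) + s/g]

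**Lag under each meaning of treated**
- Started: L = 8 + 12 = 20 (s = 0.769) or 12 + 12 = 24 (s = 0.923).
- Completed: L = 12 (s = 0.462).
- Due for SVR12: L = 0, so the ratio equals p.

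**Worked example, g = 1.25**
- Started, 12-week course: 0.9 × (0.077 + 0.923/1.25) = 0.9 × 0.815 = 73%.
- Completed: 0.9 × (0.538 + 0.462/1.25) = 0.9 × 0.908 = 82%.

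| g per half-year | Started (8 / 12-week course) | Completed | Due for SVR12 |
|---|---|---|---|
| 0.80 | 107% / 111% | 100% | 90% |
| 1.00 | 90% / 90% | 90% | 90% |
| 1.05 | 87% / 86% | 88% | 90% |
| 1.10 | 84% / 82% | 86% | 90% |
| 1.25 | 76% / 73% | 82% | 90% |
| 1.50 | 67% / 62% | 76% | 90% |

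**Pooled periods.** When windows are added up, the inner terms cancel:

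Pooled rate = p × [1 - s × (N(last) - N(before)) / total]

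Here N(before) is the half-year before the study. Two assumed paths of starts follow. Both totals lie below the plan's infected pool of 0.29 × 2,800 = 812.
- Gentle path: 50 before; then 50, 55, 60, 66, 73, 80 (384 in Years 1-3); then 73, 66, 60, 55, 50, 45 (733 in all). Years 1-3: 0.9 × [1 - s × 30/384] = 84-85%. Six years: 0.9 × [1 + s × 5/733] = 90-91%.
- Steep path: 40 before; then 40, 60, 80, 100, 100, 100 (480); then 80, 60, 40, 30, 20, 20 (730). Years 1-3: 0.9 × [1 - s × 60/480] = 80-81%. Six years: 0.9 × [1 + s × 20/730] = 92%.

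**Infection rate.** Here the passages have to be read side by side. Section 6.1 extracts both dates. Section 6.2 calculates the rate and only then destroys the core data, so events and time at risk can be assigned to calendar periods before anything is removed. No section says that infections are counted by year of re-test.

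**The case against.** The case against is substantial.

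- **The listed outcome is a count.** Table 2 asks for numbers, and those stay correct. The primary outcome does not rest on a same-window ratio. This stands, and it limits the point to the period cure rate in section 6.2.
- **Treated is not defined.** Section 6.1 itself separates patients undergoing treatment from those who have completed it. On the completed reading the distortion is roughly halved or less, and with patients due for SVR12 as denominator it vanishes. This stands; it is also why the denominator needs stating.
- **Growth is assumed.** No section gives treatment numbers per half-year. A reader might infer cure rates in the 60s from 50% growth, or 73-76% over Years 1-3 on the steep path with no earlier starts. The documents support neither: that growth is not stated, and section 1 describes Tayside treatment programmes already delivered or running.
- **The field list may not be exhaustive.** Section 6.1 names the clinical database as the source for treatment initiation, so a start date may exist there. That makes the remedy easier but does not put the date in the planned extract.

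A stronger reading of the destruction sentence is also tempting: that dated re-test rows will be lost and the fall in incidence therefore misplaced in time. The documents do not support it. The rate is calculated first with both dates in hand, an anonymised dataset survives for sharing, and the NHS virology records are separate from the study file. Section 12.3 has a database lock, and section 13.1 has the study data analysed on completion. What remains is an undefined term.

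**Conclusion.** The cure-rate point holds. Followed as written, sections 6.1 and 6.2 allow a ratio whose numerator and denominator come from different patients, and it moves with treatment volume. The gap from a true 90% is about 6 to 17 percentage points if treated means started and about 4 to 8 if it means completed. Those ranges rest on assumed growth of 10-25% per half-year, starts or completions spread evenly within each window, SVR12 recorded at exactly 12 weeks and, for the started reading, courses of 8-12 weeks. Steady numbers give no error, and a six-year total stays at 90-92% on the two paths shown. The damage is to the trend and to totals over the expansion years, not to the counts.

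The retention point is a precaution against an ambiguity. No loss of data and no bias in incidence has been demonstrated.

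**What to change.** 1. In section 6.1, add half-year of treatment start to the treatment extract. In section 6.2, define the cure rate as the proportion reaching SVR12 among patients who started in a given half-year, reported once SVR12 is due for all of them. Rows are not essential; counts of starts and SVR12 outcomes by start half-year are enough.
2. In section 6.2, say what the core data are. State that the anonymised last-negative date, re-test date and result, or events and person-time tabulated by calendar period at risk, are kept until the final synthesis is complete. Month- or quarter-level dates are enough: setting a date to the middle of its 13-week quarter moves it by at most about 6.5 weeks.

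**Cost.** One added field, a small retained file, and one amendment approved by the sponsor, REC and NHS R&D (section 12.1), with Caldicott approval if required. The latest cohort's cure rate is reported about six months later. Keeping rows has a privacy cost, because participants are not consented (section 5.1) and positive results may be few. If all 0.71 × 2,800 = 1,988 uninfected people were tested, 1% incidence would give about 20 a year. Coarse dates, or the tabulated alternative, address this.

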7 STATISTICS AND DATA ANALYSIS

7.1 SAMPLE SIZE CALCULATION

All those eligible for HCV testing and treatment in Tayside, currently estimated at 2800.

7.2 PROPOSED ANALYSES

Initially descriptive analysis will be used. In the final analysis statistical and mathematical models will develop the analytic framework that can be used to assess impact incorporating evidence from multiple sources and taking into account uncertainty and bias from our multiple data sources. We will combine Multiple Parameter Evidence Synthesis and Infectious Disease Models in order to measure the primary outcome and objective. We also will establish what ongoing surveillance and monitoring arrangements are required in future evaluations, and project impact of interventions in other settings. In addition a vital output from the data will be an economic evaluation using dynamic cost-effectiveness models of HCV treatment among PWID. These models can inform other areas and treatment scenarios.

8.3

7.3 TRANSFER OF DATA

No patient identifiable data will be transferred from NHS Tayside.

8 STUDY MANAGEMENT AND OVERSIGHT ARRANGEMENTS

8.1 STUDY MANAGEMENT GROUP

The study will be co-ordinated by a Management Group, consisting of the grant holder (CI), Study Manager, and research fellow.

8.2 STUDY STEERING COMMITTEE

A Study Steering Committee (SC) will not be established for this study. The Erapidstudy will eventually form a part of a larger study with more sites (Epitope). This larger study will compare the measures of HCV incidence in NHS Tayside, collected as part of the Erapid study, with similar measures in other regions of the UK where intensive treatment regimes for HCV infection are not currently carried out. A steering group will be established to oversee the conduct and progress of this larger study, which will include Erapid.

8.3 INSPECTION OF RECORDS

The CI will permit study related monitoring, audits, and REC review. The CI agrees to allow the Sponsor or, representatives of the Sponsor, direct access to all study records and source documentation.

9 GOOD CLINICAL PRACTICE

9.1 ETHICAL CONDUCT OF THE STUDY

The study will be conducted in accordance with the principles of good clinical practice (GCP).

In addition to Sponsorship approval, a favorable ethical opinion will be obtained from the appropriate REC and appropriate NHS R&D approval will be obtained prior to commencement of the study.

9.2 CONFIDENTIALITY

All laboratory specimens, evaluation forms, reports, and other records will be identified in a manner designed to maintain participant confidentiality. All records will be kept in a secure storage area with limited access to study staff only. Clinical information will not be released without the written permission of the participant, except as necessary for monitoring and auditing by the Sponsor or its designee. The CI and study staff involved with this study will not disclose or use for any purpose other than performance of the study, any data, record, or other unpublished, confidential information disclosed to those individuals for the purpose of the study. Prior written agreement from the Sponsor or its designee will be obtained for the disclosure of any said confidential information to other parties.

9.3 DATA PROTECTION

The CI and study staff involved with this study will comply with the requirements of the Data Protection Act 1998 with regard to the collection, storage, processing and disclosure of personal information and will uphold the Act's core principles. The CI and study staff will also adhere, if appropriate, to the current version of the NHS Scotland Code of Practice on Protecting Patient Confidentiality. Access to collated participant data will be restricted to the CI and appropriate study staff.

Computers used to collate the data will have limited access measures via user names and passwords.

Published results will not contain any personal data that could allow identification of individual participants.

9.4 INSURANCE AND INDEMNITY

The University of Dundee and Tayside Health Board are Co-Sponsoring the study.

Insurance –The University of Dundee will obtain and hold a policy of Public Liability Insurance for legal liabilities arising from the study.

Tayside Health Board will maintain its membership of the Clinical Negligence and Other Risks Insurance Scheme (“CNORIS”) which covers the legal liability of Tayside in relation to the study.

Where the study involves University of Dundee staff undertaking clinical research on NHS patients, such staff will hold honorary contracts with Tayside Health Board which means they will have cover under Tayside’s membership of the CNORIS scheme.

Indemnity Co-Sponsors do not provide study participants with indemnity in relation to participation in the Study but have insurance for legal liability as described above.

10 ADVERSE EVENTS - NOT RELEVANT TO THIS STUDY

11 ANNUAL REPORTING REQUIREMENTS

Annual reporting will be conducted in compliance with TASC SOP 15: Preparing and Submitting Progress and Safety Reports in CTIMPs and Non-CTIMPs, as a condition of sponsorship and as a condition of a favourable opinion from a REC. An HRA Annual Progress Report for NCTIMPs will be prepared and submitted by the CI to REC, and copied to the Sponsor, on the anniversary date of the REC favourable opinion.

12 STUDY CONDUCT RESPONSIBILITIES

12.1 PROTOCOL AMENDMENTS, DEVIATIONS AND BREACHES

The CI will seek approval for any amendments to the Protocol or other study documents from the Sponsor, REC and NHS R&D Office. Amendments to the protocol or other study docs will not be implemented without these approvals.

In the event that a CI needs to deviate from the protocol, the nature of and reasons for the deviation will be recorded in the CRF, documented and submitted to the Sponsor. If this necessitates a subsequent protocol amendment, this will be submitted to the Sponsor for approval and then to the appropriate REC and NHS R&D Office for review and approval.

In the event that a serious breach of GCP or protocol is suspected, this will be reported to the Sponsor Governance Office immediately

12.2 STUDY RECORD RETENTION

Archiving of study documents will be for five years after the end of study

12.3 END OF STUDY

The end of study is defined as database lock. The Sponsor or CI have the right at any time to terminate the study for clinical or administrative reasons.

The end of the study will be reported to the Sponsor and REC within 90 days, or 15 days if the study is terminated prematurely. The CI will ensure that any appropriate follow up is arranged for all participants.

A summary report of the study will be provided to the Sponsor and REC within 1 year of the end of the study.

13 REPORTING, PUBLICATIONS AND NOTIFICATION OF RESULTS

13.1 AUTHORSHIP POLICY

Ownership of the data arising from this study resides with the study team and the University of Dundee. On completion of the study, the study data will be analysed and tabulated, and a clinical study report will be prepared.

13.2 PUBLICATION

The clinical study report will be used for publication and presentation at scientific meetings. Investigators have the right to publish orally or in writing the results of the study.

Summaries of results will also be made available to Investigators for dissemination within their clinical areas (where appropriate and according to their discretion).

